6.5. Change from Protocol-Specified Efficacy Analyses

The following are added to the list of efficacy endpoints and the analyses on these endpoints are included as [REDACTED] (see Section 6.2.2):

- [REDACTED]

[REDACTED]

[REDACTED]

[REDACTED]

7. SAFETY ANALYSES

7.1. Adverse Events and Deaths

7.1.1. Adverse Event Dictionary

Clinical and laboratory AEs will be coded using a recent version of MedDRA. System organ class (SOC), high-level group term (HLGT), high-level term (HLT), preferred term (PT), and lower-level term (LLT) will be provided in the AE dataset.

7.1.2. Adverse Event Severity

The severity of AEs was graded using the modified Common Terminology Criteria for Adverse Events (CTCAE), version 4.03. For each episode, the highest grade attained should be reported. If a CTCAE criterion does not exist, the investigator should use the grade or adjectives: Grade 1 (mild), Grade 2 (moderate), Grade 3 (severe), Grade 4 (life-threatening) or Grade 5 (fatal) to describe the maximum intensity of the adverse event. For purposes of consistency with the CTCAE, these intensity grades are defined in the protocol in [Table 7-1](#) and [Appendix 5](#). The severity grade of events for which the investigator did not record severity will be categorized as “missing” for tabular summaries and data listings. The missing category will be listed last in summary presentation.

7.1.3. Relationship of Adverse Events to Study Drug

Related AEs are those for which the investigator selected “Related” on the AE CRF to the question of “Related to Study Treatment.” Events for which the investigator did not record relationship to study drug will be considered related to study drug for summary purposes. However, by-subject data listings will show the relationship as missing.

7.1.4. Action Taken With Study Drug

Action taken is recorded for multiple study treatments on the AE CRF. In adverse event summaries a worst-case approach will be applied using all available information. For example, if for at least one of the study treatments “Drug Withdrawn” was recorded, the AE will be categorized as “leading to premature discontinuation of study drug”.

7.1.5. Serious Adverse Events

Serious adverse events (SAEs) will be identified and captured as SAEs if the AEs met the definitions of SAEs that were specified in the study protocol. SAEs captured and stored in the clinical database will be reconciled with the SAE safety database before data finalization.

7.1.6. Treatment-Emergent Adverse Events

7.1.6.1. Definition of Treatment-Emergent Adverse Events

Treatment-emergent adverse events (TEAEs) are defined as 1 or both of the following:

- Any AEs with an onset date on or after the study drug start date and no later than 30 days after permanent discontinuation of study drug
- Any AEs leading to premature discontinuation of study drug.

7.1.6.2. Incomplete Dates

If the onset date of the AE is incomplete and the AE stop date is not prior to the first dosing date of study drug, then the month and year (or year alone if month is not recorded) of onset determine whether an AE is treatment emergent. The event is considered treatment emergent if both of the following 2 criteria are met:

- The AE onset date is the same as or after the month and year (or year) of the first dosing date of study drug, and
- The AE onset date is the same as or before the month and year (or year) of the date corresponding to 30 days after the date of the last dose of study drug

An AE with completely missing onset and stop dates, or with the onset date missing and a stop date later than the first dosing date of study drug, will be considered to be treatment emergent. In addition, an AE with the onset date missing and incomplete stop date with the same or later month and year (or year alone if month is not recorded) as the first dosing date of study drug will be considered treatment emergent.

7.1.7. Summaries of Adverse Events and Deaths

Treatment-emergent AEs will be summarized based on the Safety Analysis Set.

No formal statistical testing is planned.

7.1.7.1. Summaries of AE incidence in Combined Severity Grade Subsets

A brief, high-level summary of the number and percentage of subjects who experienced at least 1 TEAE in the categories described below will be provided by treatment group. All deaths observed in the study will also be included in this summary.

The number and percentage of subjects who experienced at least 1 TEAE will be provided and summarized by SOC, PT, and treatment group. The same summary is provided for the other AE categories described below.

- TEAEs with Grade 3 or higher
- TEAEs with Grade 2 or higher
- Treatment-emergent (TE) treatment-related AEs
- TE treatment-related AEs with Grade 3 or higher
- TE treatment-related AEs with Grade 2 or higher
- TE SAEs
- TE treatment-related SAEs
- TEAEs leading to premature discontinuation of study drug
- TEAEs leading to premature discontinuation of study
- TE AEs leading to death (ie, outcome of death)
- TEAEs leading to temporary interruption of study drug

Multiple events will be counted only once per subject in each summary. Adverse events will be summarized and listed in descending order of frequency, first by SOC, then by PT and then alphabetically. For summaries by severity grade, the most severe grade will be used for those AEs that occurred more than once in an individual subject during the study.

In addition to the above summary tables, the following TEAEs will be summarized by PT only, in descending order of total frequency:

- TEAEs
- TEAEs with Grade 3 or higher
- TE SAEs
- TEAEs leading to premature discontinuation of study drug.

In addition, data listings will be provided for the following:

- All AEs, indicating whether the event is treatment emergent
- All SAEs
- All Deaths
- All SAEs leading to death (ie, outcome of death)

- All AEs with severity of Grade 3 or higher
- All AEs leading to premature discontinuation of study drug
- All AEs leading to premature discontinuation of study
- All AEs leading to temporary interruption of study drug

In addition, an XML file will be created to support EUDRACT reporting for the final analysis containing serious AEs, non-serious AEs and non-serious AEs occurring in at least 5% of subjects in at least one treatment arm, either at system organ class level or at PT level. (This XML file will be created in-house).

7.1.8. Adverse Events of Interest

Adverse events of interest (AEI) include infections, gastrointestinal perforations, herpes zoster, malignancies (excluding non-melanoma skin cancers), non-melanoma skin cancers, major adverse cardiovascular events (MACE), and thromboembolic events. Summaries of the following treatment-emergent AEI will be produced to enhance the analysis of safety data.

- Events of infections presented in the following subcategories:
 - AEs of infections, utilizing all AEs in the MedDRA Infections and Infestations SOC
 - AEs of serious infections, using all AEs in the MedDRA Infections and Infestations SOC that are classified as SAEs
 - AEs of herpes zoster, utilizing an MST list developed by the Sponsor
 - AEs of opportunistic infections, utilizing a narrow scope SMQ
- AEs of malignancies, excluding non-melanoma skin cancers, utilizing an MST list developed by the Sponsor
- AEs of non-melanoma skin cancers, utilizing an MST list developed by the Sponsor
- AEs of gastrointestinal perforation, utilizing an MST list developed by the Sponsor
- AEs of MACE, utilizing a positively adjudicated event list, presented in the following subcategories (Section 7.1.8.1):
 - Cardiovascular (CV) death
 - Non-fatal myocardial infarction (MI)
 - Non-fatal stroke
- AEs of arterial systemic thromboembolism (ASTE), utilizing a positively adjudicated event list (Section 7.1.8.1)

- AEs of venous thromboembolism (VTE), utilizing a positively adjudicated event list, presented in the following subcategories (Section 7.1.8.1):
 - Venous Thrombotic and Embolic Events
 - Other

The number and percentage of subjects with a reported event will be summarized for each treatment group by PT for each AEI category. Data listings for AEI will also be provided.

A by-subject listing for subjects with potential events for adjudication (MACE, ASTE, and VTE) and their respective adjudication results will be provided.

A by-subject listing of thromboembolic history and risk factors will be provided for subjects with potential events for adjudication (MACE, ASTE, and VTE).

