3.2. Subject Grouping

For analyses based on the Safety Analysis Set and [REDACTED], subjects will be grouped according to the actual treatment received. The actual treatment received will differ from the assigned treatment only when their actual treatment differs from assigned treatment for the entire treatment duration.

For analyses of baseline characteristics and efficacy endpoints in the subset of subjects who rolled over into the LTE due to failure to meet response/remission criteria at W10 (see Section 3.4 and Section 6.3), subjects will be grouped according to the actual treatment received in both the parent study and the LTE study.

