7.2.2.3. Summaries of Laboratory Abnormalities

The following summaries (number and percentage of subjects) for treatment-emergent laboratory abnormalities will be provided by lab test and treatment group; subjects will be categorized according to the most severe postbaseline abnormality grade for a given lab test:

- Graded laboratory abnormalities
- Grade 3 or 4 laboratory abnormalities
- Marked laboratory abnormalities

For all summaries of laboratory abnormalities, the denominator is the number of subjects with nonmissing postbaseline values up to 30 days after last dosing date.

A by-subject listing of treatment-emergent Grade 3 or 4 laboratory abnormalities will be provided by subject ID number and time point in chronological order. This listing will include all test results that were collected throughout the study for the lab test of interest, with all applicable severity grades displayed.

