7.2.3. Liver-Related Laboratory Evaluations

Liver-related abnormalities after initial study drug dosing will be examined and summarized using the number and percentage of subjects who were reported to have the following laboratory test values for postbaseline measurements:

- Aspartate aminotransferase (AST): (a) > 3 times of the upper limit of normal (ULN) reference range; (b) $> 5 \times \text{ULN}$; (c) $> 10 \times \text{ULN}$; (d) $> 20 \times \text{ULN}$
- Alanine aminotransferase (ALT): (a) $> 3 \times \text{ULN}$; (b) $> 5 \times \text{ULN}$; (c) $> 10 \times \text{ULN}$; (d) $> 20 \times \text{ULN}$
- AST or ALT $> 3 \times \text{ULN}$ and total bilirubin $> 2 \times \text{ULN}$

The summary will include data from all postbaseline visits up to 30 days after the last dose of study drug. For individual laboratory tests, subjects will be counted once based on the most severe postbaseline values. For both the composite endpoint of AST or ALT and total bilirubin, subjects will be counted once when the criteria are met at the same postbaseline visit date. The denominator is the number of subjects in the Safety Analysis Set who have nonmissing postbaseline values of all relevant tests at the same postbaseline visit date. A listing of subjects who met at least 1 of the above criteria will be provided.

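### Adverse events, events of interest and categorical laboratory abnormalities are reported only as percentages of subjects, although follow-up differs between treatment columns by design and exposure is never linked to events

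*SAP*

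**What the plan says.** SAP 7.1.7.1 sets the general measure: "The number and percentage of subjects who experienced at least 1 TEAE will be provided and summarized by SOC, PT, and treatment group". The same table is repeated for serious, related, higher-grade, fatal and drug-stopping events, with each subject counted once. Deaths are not tied to the treatment window: "All deaths observed in the study will also be included in this summary". SAP 7.1.8 applies the same measure to infections, malignancy, perforation, MACE and thromboembolism: "The number and percentage of subjects with a reported event will be summarized for each treatment group by PT for each AEI category".

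For graded laboratory abnormalities (SAP 7.2.2.3), subjects are classed by worst grade, by treatment group, and "the denominator is the number of subjects with nonmissing postbaseline values up to 30 days after last dosing date". For liver abnormalities (SAP 7.2.3), "The summary will include data from all postbaseline visits up to 30 days after the last dose of study drug". That section does not name treatment group. The grouping follows only from the general rule in SAP 3.2 that "subjects will be grouped according to the actual treatment received".

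The window for a treatment-emergent event (SAP 7.1.6.1) is an "onset date on or after the study drug start date and no later than 30 days after permanent discontinuation of study drug", plus any event that led to stopping study drug. Duration of exposure is summarised by treatment group in SAP 4.2.1, as a separate table.

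On follow-up, Protocol 3.3 and 6.7 have placebo subjects stop drug and leave the study after unblinding, while filgotinib subjects continue open-label at the same dose. Protocol 3.4 allows treatment until commercial availability in the country or 31 January 2025, about 7.5 years at most.

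**The concern.** The percentage of subjects with at least one event rises with time observed, even when the underlying risk is constant. It describes columns fairly only if they are observed for similar times. Here they need not be, for three reasons:

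- **Exit.** Only the placebo column has a forced stop at parent-study unblinding.
- **Entry.** In Protocol Table 3-1, placebo in the extension goes only to subjects who completed the parent study. Under Protocol 6.2.1, subjects from GS-US-419-3895 who complete enter after Week 58, whereas non-responders enter open-label filgotinib after Week 11. That is 58 − 11 = 47 weeks earlier relative to parent-study start.
- **Window.** It closes 30 days after last dose, so each subject's chance of being counted grows with time on drug.

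These tables are the main output of a study whose primary objective is long-term safety. Events such as malignancy and MACE are ones where duration matters most. A reader comparing columns could take a difference in follow-up for a difference in risk, or miss a real difference that follow-up hides.

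**Working it through.** **What the documents supply.** There is no sample size calculation, assumed event rate, unblinding date or mean exposure per column, so no plan figure can be reproduced. SAP 7.1 to 7.5 is readable. It contains no person-years, event rates, time-to-event analysis of events or incidence by interval. Time-to-event analysis appears only as a generic example in SAP 3.8.3.

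**Illustration 1: constant hazard, equal true risk.** All rates and times are assumptions; time includes the 30-day tail. Percentage with an event = 1 − exp(−rate × years).

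| Assumed rate per 100 patient-years | 1 year | 4 years | Ratio, 4 y to 1 y | 3 years | 1.5 years | Ratio, 1.5 y to 3 y |
|---|---|---|---|---|---|---|
| 0.5 | 0.50% | 1.98% | 3.97 | 1.49% | 0.75% | 0.50 |
| 2 | 1.98% | 7.69% | 3.88 | 5.82% | 2.96% | 0.51 |
| 5 | 4.88% | 18.13% | 3.72 | 13.93% | 7.23% | 0.52 |

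With 3 years in both columns the ratio is 1.00 and nothing is distorted.

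**Illustration 2: true risk halved in the longer column.** At 2 per 100 patient-years for 1 year, the percentage is 1 − exp(−0.02) = 1.98%. At 1 per 100 patient-years for 4 years, it is 1 − exp(−0.04) = 3.92%. The safer column shows about twice the percentage. First-event rates return 2.0 and 1.0.

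**Illustration 3: why one rate is not enough.** Take a hazard of 0.20 per year in year 1 and 0.02 thereafter, the same in both columns, followed 1 and 4 years.

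- Percentages: 1 − exp(−0.20) = 18.1% and 1 − exp(−0.26) = 22.9%.
- Patient-years at risk per subject: 0.1813/0.20 = 0.906, and 0.906 + 0.8187 × (1 − exp(−0.06))/0.02 = 3.290.
- Single rates per 100 patient-years: 18.13/0.906 = 20.0 and 22.89/3.290 = 7.0.
- By interval: 20.0 in year 1 in both columns, then 2.0 in years 2 to 4 for the column still followed.

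The single rate misleads more than the percentage here; the interval rates agree.

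**Laboratory sampling.** Protocol 3.2 schedules visits at Weeks 2, 4 and 12 and every 12 weeks after that. That is 3 visits in the first 12 weeks and 1 per 12 weeks later: 6 by Week 52, against 4 in Weeks 53 to 104. A single rate of laboratory abnormalities would partly reflect visit density.

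**Partial dates.** SAP 7.1.6.2 settles only whether an event is emergent: "then the month and year (or year alone if month is not recorded) of onset determine whether an AE is treatment emergent". It assigns no onset date, which a rate would need.

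**The case against.** **The plan follows the protocol.** Protocol 8.6.2 asks for counts and percentages, and the objective is to observe. This stands: the point is an added analysis, not a contradiction, and the percentages should stay.

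**Nothing is tested or randomised.** SAP 1.3 and 3.5 plan no test, and Protocol 6.1 assigns dose by parent regimen and reason for exit. This also stands. A reader might infer that a formal comparison is biased, or that rates would make the columns comparable. The documents support neither. A descriptive table should still not let observation time pass for risk.

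**A reader can divide by the exposure table.** Partly right. In the 4-year illustration, events over total time give 7.69/4 = 1.92 per 100 patient-years against a true 2.0 (4% low). The shortfall is about 1% at a rate of 0.5 and 9% at a rate of 5. This approximation suits rare events only. It ignores time to first event and the 30-day tail, and leaves the reader to do the sum.

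**The size is unknown.** Correct. A reader might infer from the 3.9-fold example that filgotinib percentages will be inflated by that much. The inputs are assumed, and the ratio is 1.0 with equal follow-up and 0.51 in the reversed case. At the first interim, timed by SAP 2.1 to the final analysis of GS-US-419-3895, the forced stop will have had little effect on subjects from that study.

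**Rates bring their own problems.** Illustration 3 concedes this. Narrow intervals would also be sparse: with an assumed 300 subjects in a column, 48 weeks (0.92 years) gives about 300 × 0.92 × 0.005 = 1.4 events at 0.5 per 100 patient-years and 5.5 at 2. Intervals should therefore be broad and shown only where counts allow.

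**Conclusion.** The omission is established from the text. SAP 7.1.7.1, 7.1.8 and 7.2.2.3 use only counts and percentages of subjects by treatment group. SAP 7.2.3 uses the same measure, with grouping by inference from SAP 3.2. Unequal follow-up is also established, since only placebo subjects are made to leave at unblinding. The separate exposure table can reveal an imbalance but does not carry it into the event tables.

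Confidence is high in the omission and does not extend to the size or net direction of any distortion. Entry time and dropout can push either way, and the illustrations rest on assumed rates and times. The consequence is a possibly misleading description of the primary outcome, with no error rate affected. It should be fixed. Summaries by visit (continuous laboratory values, vital signs, ECG) are not part of this point.

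**What to change.** Keep all the percentages. In SAP 7.1.7 and 7.1.8:

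- Add by treatment group the patient-years at risk and the subjects with a first event per 100 patient-years, with exact Poisson 95% confidence intervals. Do this for serious events, deaths, events leading to discontinuation of study drug, and each category of interest.
- End time at risk at the earliest of first event, death, study withdrawal or last contact, 30 days past last dose, or data cut. Events outside that window, including later deaths and events that are emergent only because they led to stopping drug, stay in the counts with a footnote.
- Show these rates by broad exposure interval where counts allow, for example the first 48 weeks and later.
- Add one rule imputing onset for partial or missing event dates.
- State that the columns are non-randomised with unequal follow-up, so the rates are descriptive.

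For any treatment-emergent event, and for SAP 7.2.2.3 and 7.2.3, show total patient-years beside the percentages and no single rate.

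Optionally, if placebo is shown beside filgotinib, add a summary limited to time before parent-study unblinding. It would cover subjects from GS-US-419-4015, -4016 and -3895 and needs the unblinding dates.

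The cost is SAP wording, some programming and a few extra table columns. Nothing new is collected from subjects. SAP section 1 allows changes after finalisation to be documented in the study report.

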7.1.8.1. Cardiovascular Safety Endpoint Adjudication Committee

An independent cardiovascular safety endpoint adjudication committee (CVEAC) was formed to periodically review and adjudicate all potential MACE and thromboembolic events in a blinded manner. To identify potential MACE and thromboembolic events, the following AEs were sent for adjudication. Refer to the Cardiovascular Event Adjudication Charter for more details.

- All AEs leading to death
- CV events (meeting seriousness criteria), utilizing an MST list developed by the Sponsor
- MI, utilizing a narrow scope SMQ
- Unstable angina (meeting hospitalization criteria), utilizing an MST list developed by the Sponsor
- Transient ischemic attack, utilizing an MST list developed by the Sponsor
- Stroke, utilizing an MST list developed by the Sponsor
- Cardiac failure (meeting hospitalization criteria), utilizing an MST list developed by the Sponsor
- Percutaneous coronary intervention, utilizing an MST list developed by the Sponsor
- Embolic and thrombotic events, utilizing a narrow scope SMQ

The CVEAC will review the above AEs, and related clinical data to adjudicate whether the criteria for MACE (CV death, MI, and/or stroke), ASTE, and VTE have been met for each AE.

7.2. Laboratory Evaluations

Laboratory data collected during the study will be analyzed and summarized using both quantitative and qualitative methods. Summaries of laboratory data will be provided for the Safety Analysis Set and will include data collected up to the last dose of study drug plus 30 days for subjects who have permanently discontinued study drug, or all available data at the time of the database snapshot for subjects who were ongoing at the time of an interim analysis. The analysis will be based on values reported in conventional units. When values are below the LOQ, they will be listed as such, and the closest imputed value will be used for the purpose of calculating summary statistics as specified in Section 3.7. Hemolyzed test results will not be included in the analysis, but they will be listed in by-subject laboratory listings.

A by-subject listing for laboratory test results will be provided by subject ID number and time point in chronological order for hematology, serum chemistry, urinalysis, lipid profile, and serum immunoglobulin separately. Values falling outside of the relevant reference range and/or having a severity grade of 1 or higher on the CTCAE severity grade will be flagged in the data listings, as appropriate.

Hematocrit results collected from local laboratories due to COVID-19 impact will not be included in the safety laboratory summary, but will be included in the listing with a flag to indicate which records were collected at local laboratories.

No formal statistical testing is planned.

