## **6.5. Post-Treatment Assessments ( $\pm$ 3 days)**

All subjects must complete the Post-Treatment (PTx) assessments 30 days after the last dose of study drug.

The following evaluations are to be completed:

- Symptom-directed PE
- Complete perianal fistulae assessment (for subjects rolling over from GS-US-419-4016 **only**)
- Obtain weight
- Review AEs and concomitant medications
- Obtain vital signs (resting blood pressure, respiratory rate, pulse and temperature)
- Obtain blood samples (reference Study Procedures Table [[Appendix 2](#)])
- Obtain urine sample (reference Study Procedures Table [[Appendix 2](#)])

— Sample will be used for pregnancy test (for females of childbearing potential only)

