## 8.9. Sample Size

No formal hypothesis testing is planned for this study and sample size calculation is not conducted. All subjects who have completed or met protocol specified discontinuation criteria in a prior filgotinib treatment study for CD may enroll in this long-term extension study.

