3.8.2. Analysis Visit Windows

Subject visits might not occur on protocol-specified days. Therefore, for the purpose of analysis, observations will be assigned to analysis windows.

The analysis windows for CDAI, PRO2, vital signs, weight, hematology, and chemistry are provided in Table 3-1. The analysis windows for lipid profile, serum immunoglobulin, [REDACTED] [REDACTED] are provided in Table 3-2. The analysis windows for [REDACTED]

Table 3-1. Analysis Visit Windows for CDAI, PRO2, Vital Signs, Weight, Hematology and Chemistry

Nominal Visit	Nominal Study Day	Visit Window Study Day	
		Lower Limit	Upper Limit
Baseline	1	(none)	1
Week 2	15	2	22
Week 4	29	23	57
Week 12	85	58	127
Week 24	169	128	211
Week 36	253	212	295
Week 48	337	296	379
Week 60	421	380	463
Week 72	505	464	547
Week 84	589	548	631
Week 96	673	632	715
Week 108	757	716	799
Week 120	841	800	883

Nominal Visit	Nominal Study Day	Visit Window Study Day	
		Lower Limit	Upper Limit
Week 132	925	884	967
Week 144	1009	968	1051
Week 156	1093	1052	1135
Week 168	1177	1136	1219
Week 180	1261	1220	1303
Week 192	1345	1304	1387
Week 204	1429	1388	1471
Week 216	1513	1472	1555
Week 228	1597	1556	1639
Week 240	1681	1640	1723
Week 252	1765	1724	1807
Week 264	1849	1808	1891
Week 276	1933	1892	1975
Week 288	2017	1976	2059
Week 300	2101	2060	2143
Week 312	2185	2144	2227
Week 324	2269	2228	2311
Week 336	2353	2312	2395
Week 348	2437	2396	2479
Week 360	2521	2480	2563
Week 372	2605	2564	2647
Week 384	2689	2648	2731
Week 396	2773	2732	2815
Week 408	2857	2816	2899
Week 420	2941	2900	2983
Week 432	3025	2984	≥ 3025

CDAI = Crohn's Disease Activity Index; PRO2 = patient reported outcome consisting of 2 items: abdominal pain severity and liquid stool frequency

Table 3-2. Analysis Visit Windows for Lipid Profile, Serum Immunoglobulin,

Nominal Visit	Nominal Study Day	Visit Window Study Day	
		Lower Limit	Upper Limit
Baseline	1	(none)	1
Week 24	169	2	253
Week 48	337	254	421
Week 72	505	422	589
Week 96	673	590	757
Week 120	841	758	925
Week 144	1009	926	1093
Week 168	1177	1094	1261
Week 192	1345	1262	1429
Week 216	1513	1430	1597
Week 240	1681	1598	1765
Week 264	1849	1766	1933
Week 288	2017	1934	2101
Week 312	2185	2102	2269
Week 336	2353	2270	2437
Week 360	2521	2438	2605
Week 384	2689	2606	2773
Week 408	2857	2774	2941
Week 432	3025	2942	≥ 3025

3.8.3. Selection of Data in the Event of Multiple Records in an Analysis Visit Window

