Depending on the statistical analysis method, single values may be required for each analysis window. For example, change from baseline by visit usually requires a single value, whereas a time-to-event analysis would not require 1 value per analysis window.

If multiple valid, nonmissing measurements exist in a postbaseline analysis window, records will be chosen based on the following rules if a single value is needed:

- The record closest to the nominal day for that visit will be selected.
- If there are 2 records that are equidistant from the nominal day, the later record will be selected.
- If there is more than 1 record on the selected day, the average will be taken for continuous data and the worse severity will be taken for categorical data, unless otherwise specified.

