7.2.2.1. Treatment-Emergent Laboratory Abnormalities

Treatment-emergent laboratory abnormalities are defined as values that increase at least 1 toxicity grade from baseline at any postbaseline time point, up to and including the date of last dose of study drug plus 30 days for subjects who permanently discontinued study drug, or the last available date in the database snapshot for subjects who were still on treatment at the time of an interim analysis. If the relevant baseline laboratory value is missing, any abnormality of at least Grade 1 observed within the time frame specified above will be considered treatment emergent.

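### Labs drawn at the post-treatment visit can be reported as scheduled-week values, because the SAP has no post-treatment analysis visit and no on-drug condition when it selects records

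*SAP*

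**What the plan says.** Protocol 6.5 states: "All subjects must complete the Post-Treatment (PTx) assessments 30 days after the last dose of study drug". Its heading allows 3 days either side, and Appendix 2 marks hematology, chemistry, vital signs and weight in the PTx column. Lipids and immunoglobulins are not marked there.

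SAP 3.8.2 assigns records to visits by study day: "Therefore, for the purpose of analysis, observations will be assigned to analysis windows". Table 3-1, which covers labs, vital signs and weight, runs from Baseline to Week 432 with each window starting the day after the previous one ends. It has no post-treatment row.

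When several records share a window, SAP 3.8.3 says: "The record closest to the nominal day for that visit will be selected". Ties go to the later record. Nothing requires the subject to be on drug.

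For laboratory data, SAP 7.2 limits the summaries, which "will include data collected up to the last dose of study drug plus 30 days for subjects who have permanently discontinued study drug". SAP 7.2.2.1 uses the same limit for treatment-emergent abnormalities: "up to and including the date of last dose of study drug plus 30 days". SAP 7.3, on body weight and vital signs, uses the same selection rule but states no cut-off.

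**The concern.** Two rules interact badly at the PTx visit.

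- **Days 27-30.** A PTx lab passes the 30-day cut-off and has nowhere to go except a scheduled-week window. It may be the only record there, or it may displace an on-drug ET value that lies further from the nominal day.
- **Days 31-33.** A lab from the same permitted visit appears in no laboratory summary. On the wording of SAP 7.3, vital signs taken the same day would be kept.

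Safety, including laboratory tests and vital signs, is the primary endpoint. The by-visit change tables and the median plots of SAP 7.2.1 are its main numeric displays. A reader of a Week 36 row will take it to describe subjects treated to about Week 36, while some values may come from subjects about four weeks off drug.

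**Working it through.** The plan gives no figure to reproduce: the study is descriptive (Protocol 8.9: "No formal hypothesis testing is planned for this study and sample size calculation is not conducted"). The check is date arithmetic on the stated rules.

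**Inputs**
- PTx visit: 30 ± 3 days after last dose, so days 27 to 33 (Protocol 6.5).
- Laboratory cut-off: last dose + 30 days (SAP 7.2).
- Windows: from Week 24 on, nominal day N covers N−41 to N+42, which is 84 days (SAP Table 3-1). Week 24 is N = 169, days 128-211; Week 36 is N = 253, days 212-295.
- Selection: nearest to N, ties to the later record (SAP 3.8.3).
- Assumptions: scheduled labs fall on nominal days, the ET lab is drawn on the last-dose day, and stop days are spread evenly. The protocol does not fix the ET day relative to the last dose.

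**Step 1: the cut-off against the permitted visit.** Days 27-30 are inside (4/7 = 57%) and days 31-33 outside (3/7 = 43%). With draws peaked at day 30 (weights 1, 2, 3, 4, 3, 2, 1), the share outside is (3+2+1)/16 = 37.5%.

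**Step 2: which PTx labs are selected.** Let o be the last-dose day minus N, and let the PTx lab fall k days later, k = 27 to 30.
- If o + k > 42, the PTx lab falls in the next window and is the only record there.
- If o < 0 and |o + k| ≤ |o|, it displaces the ET lab in the same window.
- If o ≥ 0 and o + k ≤ 42, the scheduled lab at N is nearer and the PTx lab is not selected.

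| k | Alone in next window | Displaces ET lab | Selected, of 84 stop days |
|---|---|---|---|
| 27 | 27 | 28 | 55 (65.5%) |
| 28 | 28 | 28 | 56 (66.7%) |
| 29 | 29 | 27 | 56 (66.7%) |
| 30 | 30 | 27 | 57 (67.9%) |

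Over the four days, 224/336 = 66.7% are selected: 114/336 = 33.9% alone and 110/336 = 32.7% by displacement. The other third are not selected. At k = 30 that third is every stop from 14 days before to 12 days after a nominal day (27 of 84).

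As a share of all PTx labs, with draws uniform over days 27-33, this is 4/7 × 2/3 = 38%.

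**Step 3: sensitivity to the ET lab (k = 30 unless stated).**
- ET lab 7 days after last dose: 63%.
- ET lab 14 days after last dose: 60%.
- No ET lab: 81% (k = 27) to 85% (k = 30).

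**Step 4: single cases.**
- Last dose day 200, PTx day 230: this is the Week 36 value, with no on-drug record in the window. Drawn on day 231, it is excluded from the summaries.
- Last dose and ET lab day 230, PTx day 260: the PTx lab is 7 days from day 253 and the ET lab 23 days, so the off-drug value is used.
- Last dose day 169, PTx day 199: the Week 24 lab is at distance 0 and the PTx lab at 30, so the PTx lab is not used.

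**The case against.** The strongest reply is that little follows from this in practice, and much of it stands.

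- **Stops may cluster at visits.** Subjects are seen and supplied every 12 weeks, and Protocol 6.7 brings placebo subjects in at their next scheduled visit or earlier. The two-thirds figure depends on evenly spread stop days, and clustering at visits pushes it toward zero.
- **The 30-day limit is the protocol's.** Protocol 8.6 also summarizes safety data up to 30 days after last dose, and adverse events use the same limit. A reader might infer that the SAP contradicts the protocol. It does not; the mismatch lies between that limit and the protocol's own visit tolerance.
- **Nothing is lost from the record.** A reader might infer that day 31-33 results vanish. Protocol 8.6 lists all data, and SAP 7.2 flags out-of-range and graded values in the listings.
- **The direction of bias is open.** It is tempting to say that off-drug values pull drug effects toward zero. That assumes an off-drug baseline. Under SAP 3.8.4, baseline is the last value on or before the first dose in this study, and under Protocol Table 3-1 blinded filgotinib completers continue their regimen. For them a washed-out value could add change. Protocol 1.4 also reports no clear clinical shift in neutrophils, lymphocytes or hemoglobin that could be diluted.
- **Medians are robust.** The planned plots show medians and quartiles, which a few records hardly move at well-filled visits.

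None of this supplies a rule that keeps PTx records out of the Week windows. The mislabelling remains even where its numerical effect is small.

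**Conclusion.** The point holds as a minor defect in the by-visit displays. PTx hematology and chemistry from days 27-30 are eligible to be scheduled-week values. They are chosen for about two-thirds of stop days (66-68% by draw day) if last doses are evenly spread and an ET lab is drawn at the last dose. The range is about 60% to 85% under other ET timings. With an ET lab at the last dose, it is none when dosing stops at or within about two weeks of a nominal visit from Week 12 on. It would therefore be wrong to infer that every eligible PTx lab is reported as a scheduled-week value.

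Days 31-33, three of the seven permitted days, are left out of the laboratory summaries but remain listed. SAP 7.3 is silent on a cut-off for vital signs and weight. That silence should not be read as a decision to keep them without limit, since Protocol 8.6 covers all safety data.

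The documents give no discontinuation rate, so the off-drug share of any visit row cannot be sized from them. Neither the sign of the distortion nor a material effect on the medians is established.

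**What to change.** In SAP 3.8.2, assign PTx records for labs, vital signs and weight to a separate post-treatment analysis visit covering days 27-33 after last dose. Identify them by visit label rather than study day, and exclude them from selection for the Week windows. Add a clause to SAP 7.2 letting that row take draws through day 33, and refer to the same rule in SAP 7.3. All 7 permitted days would then be shown instead of 4, and no PTx record would fill a Week row.

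Keep the 30-day limit for treatment-emergent laboratory abnormalities. Extending labs alone to day 33 would depart from Protocol 8.6 and from the adverse-event definition: an abnormality on day 32 would count as treatment-emergent while an adverse event starting that day would not.

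The cost is a sentence or two and one extra row per table, and the final windows will hold slightly fewer records. SAP section 1 already provides for documenting later changes in the clinical study report.
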